Protocol and Statistical Analysis Plan

Official Title: **Brief Online Interventions for Alcohol Use (Mechanical Turk 10)**

NCT Number: **NCT03438539**

Document Date: **February 22, 2018**

Coversheet Created On: **November 26, 2019**

RESEARCH PROCEDURES

This experiment will consist of a battery of self-report questionnaires about health behaviors and alcohol use. Subjects will be told that the purpose of the study is to learn about the effects of cognitive training. Other than this general explanation of purpose, subjects will not be given any information concerning what outcomes might be expected.

Screening Questions (Appendix B). To determine whether subjects qualify, a short screening questionnaire will be used in which subjects answer questions about their age, sex, and drug use behaviors. Namely, subjects will be asked if they used alcohol, cigarettes, and marijuana in the past week to conceal the specific drug use qualifications. Subjects will also complete a questionnaire evaluating DSM-V criteria for alcohol use disorder. If a subject fails to qualify based on the inclusion criteria stipulated above (see Study Population), he or she will be thanked for his or her time and provided \$0.05 compensation for completing this screener.

Phase 1: Baseline Survey. Subjects will first complete a baseline phase in which a health and drug use history is collected. Approximately half of subjects will also be randomized to receive normative feedback on alcohol use as a part of the baseline survey (see Normative Feedback below).

Alcohol Use History. Subjects will complete a battery of standardized assessments of alcohol use, such as the Alcohol Use Disorder Identification Test (AUDIT), Drinker Inventory of Consequences (DrInC), and timeline follow back for the past two weeks of alcohol use (TLFB). These measures are designed to capture past and current alcohol use behaviors and severity (e.g., drinks consumed per week, past month binge alcohol use). The Readiness for Change questionnaire evaluating desire and readiness to change alcohol use behaviors will also be collected (Rollnick et al., 1992). However, no exclusion criteria based on desire or readiness to change alcohol consumption will be used.

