Behavioral Economic Measures (Appendix C-E). Subjects will complete a battery of behavioral economic measures, including a delay discounting task (Koffarnus & Bickel, 2014; Appendix C), commodity purchase task (Murphy and MacKillop, 2006; Appendix D), and a Reinforcement Survey Schedule-Alcohol Use Version (Murphy et al., 2005; Appendix E). These measures have been extensively applied in the behavioral science literature to evaluate aspects of alcohol valuation and reinforcement (Amlung et al., 2015; Murphy and MacKillop, 2006; Cox and Dallery, 2016; Koffarnus and Bickel, 2014; Morris et al., 2017). We have also effectively used these measures on the mTurk platform in previous research (Strickland & Stoops, under review; Strickland & Stoops, 2017; Strickland et al., 2017).

Normative Feedback (Appendix F). Half of subjects will be randomly assigned to a normative feedback condition. Subjects assigned to this condition will be directed to a statement standardized based on subjects' reported average number of standard drinks per week, age, and gender. This statement will provide a normative comparison of alcohol consumption to individuals of the same age and gender (see Appendix F for example). Percentile ranks for the normative comparisons will be made using data from the 2016 National Survey on Drug Use and Health (Center for Behavioral Health Statistics, 2017). After receiving feedback, subjects will report perceptions of this feedback (e.g., was it surprising, helpful, expected) as well as motivation to change alcohol use in response to the feedback. Previous studies have shown the feasibility and acceptability of delivering this type of normative feedback through mTurk (Kuerbis et al., 2016; 2017). Control participants will receive feedback on time spent doing a non-alcohol related activity as an attention/informational control (e.g., time spent watching television; LaBrie et al., 2013). Control subjects will complete feedback perception questions for the provided information, similar to the alcohol normative feedback group.

Demographic and Other Drug Use Variables: A battery of standardized questionnaires will assess other drug use and health behavior (e.g., DAST for substance use severity; FTND for cigarette use severity). Demographics will be also collected for each subject, including items such as age, sex, race, and education.

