Phase 2: Cognitive Training Phase. Following completion of the baseline phase, subjects will be contacted through mTurk's interface to complete a 2-week cognitive training study. Subjects will be asked to complete daily cognitive training surveys and told that they will receive \$0.50 for each 5-8 minute survey completed. Additionally, subjects will be told that completion of 10 or more assessments will result in entry into a raffle for one of five \$50 bonuses.

Subjects will be randomly assigned to one of three training conditions using stratified sampling. Sampling will be stratified based on alcohol use disorder status (e.g., moderate, severe) to ensure equal representation in each condition. All training conditions will be completed daily and will take ~5-8 minutes to complete. Tasks will be programmed in PsyToolkit, an open-source web-based platform that provides reliable reaction time data for online delivery (Stoet, 2017). Recent research in our laboratory has effectively used PsyToolkit for

completing cognitive-behavioral research and demonstrates the feasibility of using the resource for conducting research through mTurk (Lile et al., in preparation).

Inhibitory Control Training (Appendix G). The inhibitory control training task is a modified version of the Cued Go/No-Go tasks (Weafer and Fillmore, 2012; Miller et al. 1991) and is based on a task currently used in our laboratory targeting cocaine inhibitory control. The task will take approximately 5 minutes to complete and will consist of 2 blocks of 50 trials. A trial will involve a sequence of events during which a fixation point (+) will be presented for 800 ms, followed by a blank white screen for 500 ms, a cue image (alcohol or neutral) will be presented for one of five stimulus onset asynchronies (SOA; i.e., 100, 200, 300, 400, 500 ms), and finally a go or no-go target, which will be displayed until a response occurs or 1000 ms elapses. There will be a 700 ms interval between all trials. Alcohol images will serve as no-go cues and visually matched neutral images will serve as go cues. Cues will predict which target will be presented 100% of the time. After a SOA, the cue will either turn solid green (go target) or solid blue (no-go target). Subjects will be instructed to press the SPACE bar on the keyboard as soon as a green (go) target appears. Subjects will be instructed to withhold responses when a blue (no-go) target appears.

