Two-Week Follow Up. Subjects will be asked to complete a 2-week follow up survey. This survey will include alcohol use and severity measures as well as 2-week timeline follow back from the end of the intervention period.

Data Analysis (Statistical Analysis Plan)

All statistical analyses will be conducted in R programming using two-tailed tests and an alpha rate of 0.05.

Feasibility. Descriptive statistics will first be used to express study attrition (i.e., the primary measure of feasibility). Feasibility will be supported by average completion rates during the intervention period greater than 80%. This value was selected given the general target of greater than 80% when evaluating adherence to pharmacological interventions (see Brown & Bussell, 2011). Predictors of attrition will also be evaluated using multiple regression (% completed assessments) or time-hazard models (time to first missed assessment).

Acceptability. Descriptive statistics will first be used to express acceptability measures. The primary outcome will be percentage of subjects reporting they would participate again. Success will be defined greater than 80% subjects reporting they would participate again in each active intervention condition. This value was selected for consistency with the feasibility benchmark selected. Other measures will be compared between cognitive-training conditions (e.g., enjoyability) using a one-way between-subjects ANOVA. Other predictors of acceptability will be evaluated using multiple regression (continuous outcomes) or logistic regression (dichotomous outcomes).

Initial Efficacy and Moderating Variables. Mixed-effect modeling (i.e., multilevel modeling) will be used to evaluate intervention effects on alcohol use. The primary outcome will be subjects with no heavy drinking days (dichotomous). This criterion was recently selected by the FDA as an acceptable clinical trial endpoint for FDA-approval of medications. Secondary outcomes will include changes in behavioral economic measures and other alcohol use variables by treatment condition. Secondary analyses will also be conducted evaluating baseline measures as prognostic variables predicting changes in alcohol consumption.

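### Training assignment is stratified by alcohol use disorder status but not by the already known feedback arm, which costs a little precision but causes no bias

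*Combined protocol and SAP*

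**What the plan says.** The first randomisation is in the Phase 1 baseline survey: "Approximately half of subjects will also be randomized to receive normative feedback on alcohol use as a part of the baseline survey". The Normative Feedback section repeats it: "Half of subjects will be randomly assigned to a normative feedback condition". Control subjects receive feedback on an activity unrelated to alcohol. Neither statement mentions stratification or blocking.

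The second randomisation is described under Phase 2: Cognitive Training Phase. That phase comes later: "Following completion of the baseline phase, subjects will be contacted through mTurk's interface to complete a 2-week cognitive training study". The allocation rule is: "Subjects will be randomly assigned to one of three training conditions using stratified sampling". The stratification factor follows: "Sampling will be stratified based on alcohol use disorder status (e.g., moderate, severe) to ensure equal representation in each condition". The words in parentheses are example levels of disorder status, not further factors. Nothing in the document describes a single scheme that assigns subjects to the six combinations of feedback and training.

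On analysis, the Data Analysis section says: "Mixed-effect modeling (i.e., multilevel modeling) will be used to evaluate intervention effects on alcohol use". It does not name feedback arm, the stratification factor, or a feedback-by-training interaction as a model term. The primary efficacy outcome is binary: whether a subject had no heavy drinking days.

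**The concern.** The plan accepts that the training arms should be balanced on a characteristic related to drinking, and it uses disorder status for this. Feedback arm is a second such characteristic. It is itself an intervention aimed at drinking, and the baseline survey records "motivation to change alcohol use in response to the feedback". It is also on record when training is assigned, so balancing on it needs no new data.

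Two quantities are at stake. First, if one training arm happens to contain more feedback subjects than another, an unadjusted difference between those arms moves by the gap in feedback share times the feedback effect. Over repeated randomisations this averages to zero, so it adds variance and not bias. Second, an uneven split within a training arm makes the feedback contrast in that arm less precise.

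**Working it through.** The plan gives no sample size, power statement or expected effect, so there is no figure of its own to reproduce.

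**From the document:** three training arms; feedback to about half of subjects; a binary primary outcome; feedback assigned before training.

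**Assumed:** n subjects per training arm (20, 30, 50, 100); feedback effect d on the primary outcome (10, 15 or 20 points); overall event rate p (20 to 50%); feedback allocated independently of training with probability 0.5.

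**Step 1. Size of chance imbalance.** The difference in feedback share between two arms has variance 2 × 0.25/n = 0.5/n. Its SD is √(0.5/n).

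| n per arm | SD of difference in feedback share | Chance of a gap of 20 points or more, one pair of arms |
|---|---|---|
| 20 | 15.8 points | 26.8% |
| 30 | 12.9 points | 15.5% |
| 50 | 10.0 points | 5.7% |
| 100 | 7.1 points | 0.6% |

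The last column is exact, from two independent binomial arms. Across all three arms, the chance that the largest gap reaches 20 points is about 50%, 33%, 14% and 2% (simulation with exactly half of subjects on feedback).

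**Step 2. What a gap does to an unadjusted training contrast.** Shift = gap × d. For a 20-point gap and d = 15 points: 0.20 × 0.15 = 3 points. For d = 10 and 20 points: 2 and 4 points. For scale, the standard error of a difference between two arms is √(2p(1−p)/n). At n = 20 this is 12.6 points for p = 20% and 15.8 points for p = 50%. A 3-point shift is thus 3/12.6 = 0.24 or 3/15.8 = 0.19 of one standard error.

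**Step 3. Share of the contrast's variance due to imbalance.** The imbalance contributes d² × 0.5/n. The total variance is 2p(1−p)/n. The ratio is 0.25d²/[p(1−p)], from which n cancels.

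| d | p = 50% | p = 20% |
|---|---|---|
| 10 points | 0.0025/0.25 = 1.0% | 0.0025/0.16 = 1.6% |
| 15 points | 0.005625/0.25 = 2.3% | 0.005625/0.16 = 3.5% |
| 20 points | 0.0100/0.25 = 4.0% | 0.0100/0.16 = 6.3% |

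These shares are on the risk-difference scale.

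**Step 4. Feedback contrasts within one training arm.** With a of n subjects on feedback, the variance relative to an even split is (1/a + 1/(n−a))/(4/n). Its mean over Binomial(n, 0.5), leaving out arms with no subject on one side, exceeds 1 by 6.0%, 3.7%, 2.1% and 1.0% at n = 20, 30, 50 and 100. If feedback is a simple coin toss, part of this comes from the overall split being uneven, which stratifying training cannot remove. The same formula applied to all 3n subjects gives 1.8%, 1.2%, 0.7% and 0.3% for that part.

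**Step 5. Effect of the change.** With two disorder levels (assumed), exactly half of subjects on feedback, and blocks of 3 or 6 within the four strata, the 95th percentile of the largest gap in feedback share among the three arms falls as follows (simulation).

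| Total subjects | Without feedback stratification | With it |
|---|---|---|
| 60 | 35 points | 8–10 points |
| 90 | 30 points | 5–7 points |
| 150 | 24 points | 3–4 points |
| 300 | 17 points | 1.5–2 points |

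No gap of 20 points or more occurred in 4,000 stratified draws per setting.

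**The case against.** The strongest reply is that nothing here is wrong. Two independent randomisations are a valid way to run a crossed design. Feedback is balanced across training arms in expectation, the training contrast is unbiased, and an ordinary test already allows for chance imbalance. All of this stands. A reader might infer from the 27% chance of a 20-point gap that the training comparison is confounded with feedback. The document does not support that reading: the gap arises by randomisation alone, and its effect on the contrast is about a fifth to a quarter of one standard error at 20 per arm.

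A second reply is that the cost applies only to an unadjusted contrast, and that a feedback term in the model would remove most of it without touching the randomisation. This also stands for the training contrast. The plan, however, neither names such a term nor says that the analysis will be unadjusted, so adjustment cannot be taken as given.

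Third, sample size and feedback effect are assumptions. That is so; the sample size may be in a part of the protocol that was not posted. The variance share in Step 3 does not depend on n, but it does depend on the feedback effect.

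Two further readings are tempting and go too far. One is that feedback is the factor most worth balancing: nothing in the document shows that it predicts drinking more strongly than disorder status does. The other is that adding it has no downside: the number of strata depends on how many disorder levels are used, and the plan gives only examples.

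**Conclusion.** The point holds as a minor design improvement. The plan leaves the balance of a known, randomised, alcohol-directed factor to chance when it could be fixed at assignment. The consequence is lost precision, not bias: about 2 to 4% of the variance of an unadjusted training contrast under a 15-point feedback effect and event rates of 20 to 50%, with 1 to 2% and 4 to 6% for effects of 10 and 20 points. Within-arm feedback contrasts lose more in small arms (6% higher variance at 20 per arm) and very little in large ones (1% at 100). The reading of the allocation rule is firm. The sizes rest on assumed sample sizes, event rates and feedback effects. Leaving the plan as it is would not invalidate the trial.

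**What to change.** In Phase 2: Cognitive Training Phase, replace the stratification sentence with wording such as: training condition will be assigned in permuted blocks of three or six within strata defined by alcohol use disorder status and feedback assignment.

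In the Data Analysis section, under initial efficacy, add that the mixed-effect model will include feedback arm as a term. Both changes are needed. If the arms are stratified on a prognostic factor that the model then ignores, standard errors are slightly too large and the precision gain is not fully realised. If only one change can be made, the model term recovers most of the loss in the training contrast.

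The cost is one more factor in the assignment program and one more model term. The strata number four with two disorder levels and six with three. With more levels and a small sample, incomplete blocks would erode the gain, so the levels should be stated.

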Working Memory Training (Appendix H for example). A battery of working memory tasks will be used during the intervention period. These tasks were selected from previous research evaluating working memory training in substance use disorder (Bickel et al., 2011b; Houben et al., 2011b). Tasks will include visuospatial working memory task, digit span task, letter span task, and the n-back task. Broadly speaking, these tasks require information recall and/or categorization of that information based on short-term retention. Task difficulty varies within each task and increases or decreases based on task performance. Subjects will complete one task randomly selected from the possible tasks during each session. Expected time of completion is 5 minutes.

Control Training Tasks. Control training tasks will include completion of basic arithmetic problems for approximately 5 minutes. These problems will include simple one digit arithmetic and are intended to control for engagement with the training session, but with a task that is unrelated to response inhibition or working memory training.

Alcohol Use Measures (Appendix J). All subjects will also report on the previous day's alcohol use and alcohol craving during each training session.

Phase 3: Follow Up Phase.

Post-Training Follow Up. Subjects will be asked to complete a post-training follow up survey. This survey will be identical to the baseline survey and will evaluate changes in the alcohol use, behavioral economic, and other cognitive-behavioral measures over the course of the 2-week training period.

The post-training follow up will also contain acceptability measures. The Treatment Acceptability Questionnaire will be administered and subjects will rate their response to statements on a 100-point visual analog scale (0 = Low; 100 = High) (e.g., ease of completion, helpful instructions, enjoyability). Multiple choice questions will also be used to evaluate how much subjects would pay to participate in the tasks completed in the study, if they would participate again, and motives related to study participation (e.g., to make money, to reduce alcohol use). Qualitative measures will also be included to collect features not captured by these quantitative measures (e.g., "What did you like most/least about the study?"). These measures were derived from prior research delivering behavioral interventions through online platforms (e.g., Raiff et al., 2013)

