Appendix I

Daily Alcohol Use Follow Up Questions

Alcohol Recall

Please enter the approximate number of each type of standard alcoholic drinks you consumed on “Monday 9/5/17**”

*Note that the date will be individualized for each survey

12 oz beer (Less than 6% ABV)
(e.g., most American beer, Budweiser, Miller)

12 oz beer (6% ABV or greater)
(e.g., most craft beer, IPA)

4 oz wine or champagne

12 oz alcopop
(e.g., wine cooler, hard lemonade, cider)

1 shot of hard liquor
(e.g., whisky, tequila)

12 oz malt liquor
(e.g., Colt 45, Steel Reserve)

1 mixed drink with 1 shot of hard liquor
(e.g., martini, margarita)

Other alcoholic beverage

Alcohol Craving (Modified version of the Penn Alcohol Craving Scale-PACS; Flannery et al., 1999)

All items measured on a 10-point scale (0 = Not at All; 10 = Constantly)

How often did these things happen over the past DAY regarding your alcohol use:

1. How often did you have a strong urge to drink alcohol?
2. How often did you picture drinking alcohol?
3. How often did you imagine what alcohol would taste like?
4. How often did you imagine how your body would feel if you had alcohol?
5. How often were the thoughts of alcohol intrusive?

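### The two drinking measures are not guaranteed to cover all 14 training days on which an all-or-none primary outcome depends

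*Combined protocol and SAP*

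**What the plan says.** **Outcome.** Under Initial Efficacy and Moderating Variables, the SAP states: "The primary outcome will be subjects with no heavy drinking days (dichotomous"). It gives no data source, assessment window, heavy-day threshold, or rule for an unreported day or a missing survey.

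**Daily reports.** Phase 2, Alcohol Use Measures: "All subjects will also report on the previous day's alcohol use and alcohol craving during each training session". The form in Appendix I asks for drinks on a single date ("Note that the date will be individualized for each survey") and shows no item for days skipped since the last report. Skipping is expected: "completion of 10 or more assessments will result in entry into a raffle", and the feasibility target is average completion above 80%.

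**TLFB.** The baseline battery includes a "timeline follow back for the past two weeks of alcohol use (TLFB"). Of the post-training survey the protocol says: "This survey will be identical to the baseline survey and will evaluate changes in the alcohol use" and other measures "over the course of the 2-week training period". The TLFB is therefore repeated after training and is meant to describe training. No calendar dates and no completion deadline are attached to it. The TLFB at the later two-week follow-up is different: its period is counted from the end of the intervention.

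**The concern.** A subject meets the outcome only if every day in the window was free of heavy drinking, so the classification can turn on one day. If the window observed differs from the training period, some subjects are scored on the wrong days. If days are blank and the handling is chosen after the data are seen, the success rate depends on that choice. The three arms do different tasks and may differ in completion, so the choice could also affect the comparison between arms. Days that no instrument asks about can be recovered later only by longer recall.

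**Working it through.** The plan states no sample size, event rate or power for this outcome, so there is no figure of its own to reproduce. The SAP sets two-tailed tests at 0.05. One daily session for two weeks is taken as 14 sessions, on days 1-14. This fits the documents: 10/14 = 71.4%, in line with the more-than-70% wording in Appendix B.

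**1. Coverage by daily reports.** Sessions on days 1-14 with previous-day recall reach days 0-13, so at most 13 of the 14 training days.
- Expected coverage at completion c is 13c: 13 × 0.80 = 10.4 days, and 13 × 0.70 = 9.1 days.
- A subject with exactly 10 sessions has 10 training days covered, or 9 if the first session is among them.

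**2. Coverage by the post-training TLFB.** Completed on day 15 + k, it reaches days 1 + k to 14 + k, so 14 - k training days.
- k = 0: 14 days. k = 3: 11 days. k = 7: 7 days.
- With daily reports at 80% completion filling the early days, coverage is 14 - k + 0.8k: 13.4 days at k = 3 and 12.6 at k = 7.
- A subject who skips this survey has daily reports only.

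**3. Effect of a TLFB three days late, scored as it stands.** Daily heavy-drinking risk is assumed, with days independent given a subject's risk. A false success has days 4-17 clear but a heavy day in days 1-3: P(0 of 14) - P(0 of 17). A false failure is the mirror image and has the same probability.
- Fixed risk 15%: 0.85^14 - 0.85^17 = 0.1028 - 0.0631 = 0.0397 each way, so 7.9% misclassified.
- Risk varying between subjects as Beta with mean 25% and concentration 4, i.e. Beta(1, 3), for which P(0 of d) = 3/(3 + d): 3/17 - 3/20 = 0.1765 - 0.1500 = 0.0265 each way, so 5.3% misclassified.
- The success rate itself does not move: 10.3% in either window under fixed risk, 17.6% in either window under the Beta model.

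**4. The same late TLFB, limited to training days, with daily reports (80% completion) filling days 1-3 and remaining blanks ignored.**
- Fixed risk: 0.85^11 × (1 - 0.8 × 0.15)^3 - 0.85^14 = 0.1140 - 0.1028 = 0.011, so about 1.1% misclassified.

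**5. Illustration only: daily reports alone, blanks ignored.** Apparent success is (1 - cp)^13 and true success is (1 - p)^14, with p the assumed daily risk.
- c = 0.80: true against apparent is 48.8% vs 58.8% (p = 0.05), 22.9% vs 33.8% (p = 0.10) and 4.4% vs 10.4% (p = 0.20).
- 90% completion in one arm, 70% in the other, no true effect: apparent success differs by 8.0, 9.6 and 6.5 points at the same three risks. The arm with lower completion looks better.

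**6. Scoring of subjects with incomplete coverage.** Beta(1, 3) model; 20% lost after seven daily reports, for reasons unrelated to drinking; truth 17.6%.
- Known failures counted, incomplete subjects with no heavy day seen left unscored: successes 0.8 × 3/17 = 0.141; unscored 0.2 × 3/10 = 0.06; rate 0.141/0.94 = 15.0%.
- All incomplete subjects counted as not meeting the outcome: 14.1%.
- Unscored subjects given their model probability of finishing without a heavy day, (3/17)/(3/10) = 0.588: 0.141 + 0.06 × 0.588 = 17.6%, the true rate.

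**The case against.** The best defence is that the protocol says what the post-training survey is for: change over the training period. A TLFB completed promptly on day 15 covers exactly days 1-14, including the day that the daily form cannot reach. After a short delay the two sources together leave a small gap (13.4 of 14 days at three days late). All arms share the same schedule, payment, raffle and approximate session length, so a large gap in completion between arms is an assumption. The raffle threshold is an incentive, not an analysis rule.

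Most of this stands, and it rules out three stronger readings that a reader might infer:
- **That neither source covers the training period.** A prompt TLFB does.
- **That blank days count as success.** The SAP has no missing-day rule and does not say that the outcome is scored from daily reports alone. Step 5 shows one possible handling, not the plan's.
- **That a late TLFB inflates success.** It still records 14 days. With stable risk its errors run equally in both directions.

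The defence does not supply a date anchor, a completion window, a statement that the two sources are combined, or any provision for subjects who skip the post-training survey. The follow-up TLFB does have an anchor, so the device was available.

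**Conclusion.** The point holds as a gap in data collection that is cheap to close. Coverage of training days 1-14 is intended but not secured. Daily reports miss day 14 and the day before every skipped session, and the TLFB covers the right days only if it is completed on time.

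A TLFB three days late misclassifies about 5% to 8% of subjects. This rests on the assumed delay and on the assumed risks (fixed 15%, or Beta with mean 25%). It is noise around an unchanged rate as long as risk is stable across the end of training; if drinking shifts when training stops, it is no longer neutral. Inflated success, larger in the arm with lower completion, would arise only if daily reports alone were used and blanks ignored. The documents neither prescribe nor exclude that. The completion rates, delays and risks used here are assumptions, because the plan gives none for this outcome.

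**What to change.** 1. **Anchor the post-training TLFB** to the 14 named training dates. This also picks up day 14 and removes the window shift when the survey is late. The statement that the survey is identical to baseline then needs a small amendment.
2. **Let the daily form catch up**: ask separately about each calendar day since the last completed report.
3. **State the scoring rule in the SAP.** Name the date-anchored TLFB as the primary source, with daily reports filling any training days that it leaves uncovered. Handle subjects who remain incomplete by one prespecified method that uses their observed days, for example multiple imputation of the missing days. A subject with an observed heavy day then stays a failure in every imputation. Add a sensitivity analysis that counts incomplete subjects as not meeting the outcome.

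Counting known failures while leaving incomplete subjects with no heavy day seen unscored should be avoided. It biases success downward even when loss is unrelated to drinking (15.0% against 17.6% in step 6).

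**Cost.** Survey programming is small because the daily form's date is already individualised, and a few sentences go into the SAP. Reports become slightly longer, and subjects must recall more than one day after a missed session, or further back when the survey is late.

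### Does the 80% acceptability benchmark need a stated denominator before it can be used?

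*Combined protocol and SAP*

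**What the plan says.** Under Data Analysis, Acceptability, the plan names its main acceptability measure: "The primary outcome will be percentage of subjects reporting they would participate again". It then attaches the pass mark: "Success will be defined greater than 80% subjects reporting they would participate again in each active intervention condition". The figure of 80 is explained in one sentence: "This value was selected for consistency with the feasibility benchmark selected". That benchmark is in the Feasibility paragraph: "Feasibility will be supported by average completion rates during the intervention period greater than 80" per cent. The same paragraph makes attrition the primary measure of feasibility and plans models for its predictors.

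The item is collected under Phase 3, Post-Training Follow Up: "The post-training follow up will also contain acceptability measures". The multiple-choice questions there cover "how much subjects would pay to participate in the tasks completed in the study, if they would participate again" and motives for taking part. The Two-Week Follow Up is described without the item: "This survey will include alcohol use and severity measures as well as 2-week timeline follow back from the end of the intervention period". The daily questions in Appendix I cover drinking and craving only.

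On allocation, Phase 2 says: "Subjects will be randomly assigned to one of three training conditions using stratified sampling". Two of the three are active: inhibitory control training and working memory training. In the public text, nothing states the denominator of the acceptability percentage or how a missing answer counts.

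**The concern.** A threshold fixed in advance guards against choosing a favourable result only if the percentage it applies to is also fixed. Here a subject who does not return the post-training survey has no answer, and the plan does not say whether that subject leaves the denominator or stays in it as not willing. The wording fits both. When Phase 2 describes allocation, the word subjects means everyone assigned. In the acceptability sentence it can equally mean those who gave an answer.

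The plan expects some loss, since attrition is itself an outcome. What would be at stake is the success statement for each active condition: an analyst who already knew the return rate could choose the denominator that passes. If non-responders were less willing to take part again, the responder percentage would also overstate willingness in the whole condition.

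**Working it through.** The plan gives no expected percentage, return rate or number per condition for this outcome, so there is no figure of its own to reproduce. The only input from the documents is the cut-off, strictly above 80%, applied in each active condition. Everything else below is assumed.

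**Condition for opposite verdicts.** Let r be the share of assigned subjects who answer the item and p the share of those answering who say yes.

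- Responder reading passes if p > 0.80.
- All-assigned reading, with no answer counted as not yes, passes if r × p > 0.80, that is, p > 0.80 / r.
- The two disagree when 0.80 < p ≤ 0.80 / r.

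| Assumed return r | 0.80 / r | Responder yes-rates with opposite verdicts |
|---|---|---|
| 98% | 0.816 | above 80%, up to 81.6% |
| 95% | 0.842 | above 80%, up to 84.2% |
| 90% | 0.889 | above 80%, up to 88.9% |
| 85% | 0.941 | above 80%, up to 94.1% |
| 80% | 1.000 | every rate above 80% |

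The last row is the edge of the range. It should not be tied to the plan's feasibility threshold, which concerns completion during the intervention period and is not a return rate for this survey.

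**Two yes-rates.**

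- p = 0.85: at 90% return, 0.90 × 0.85 = 0.765, which fails, while 85% of responders passes. At 95% return, 0.95 × 0.85 = 0.8075, and both pass.
- p = 0.90: at 90% return, 0.90 × 0.90 = 0.81, and both pass.

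**In counts, assuming 50 assigned and 45 answering.** The responder reading passes from 37 yes (37/45 = 82.2%; 36/45 = 80.0% does not exceed the mark). The all-assigned reading passes from 41 yes (41/50 = 82.0%). Counts of 37 to 40 split the readings. For example, 40/45 = 88.9% passes and 40/50 = 80.0% does not. With 40 yes, counting the 5 non-responders first as unwilling and then as willing gives 40/50 = 80.0% and 45/50 = 90.0%.

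**Chance of passing.** With the same 45 of 50 and a true responder yes-rate of 90%, the binomial probability of 37 or more yes is 96.8%, and of 41 or more it is 52.7%. For both active conditions, taken as independent, the figures are 0.968² = 93.7% and 0.527² = 27.8%.

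**The third denominator.** Subjects who started training number no more than those assigned and, if only starters answer, no fewer than those answering. For the same number of yes answers, that percentage lies between the other two and adds no new extreme.

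**Which reading the plan favours.** Feasibility is the domain in which the plan counts loss of subjects. Acceptability is a separate domain, measured by survey questions put to people taking the survey. Counting non-return as unwillingness would bring attrition into the second domain after it has been measured in the first. This structure leans towards responders, though no sentence says so. The sentence that carries the figure of 80 over from Feasibility explains only where the number came from; it is silent on missing answers.

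**The case for a change.** The strongest reply is that calling the rule descriptive does not settle the matter. The plan itself defines success on this percentage, separately for each active condition, and two competent analysts could follow the text and announce different verdicts. At moderate non-return the difference is large: 96.8% against 52.7% for one condition in the example above. Naming the denominator would take a sentence.

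Much of that stands. The denominator is unstated, the split verdict is real under the assumed return rates, and a sentence would settle it. What does not follow is that the plan as written gives a wrong answer. Both denominators are legitimate: one measures willingness among those asked, the other combines willingness with retention. The documents do not show that non-responders differ from responders, so neither the size nor the direction of any bias can be stated. The large gaps also depend on assumed return and yes-rates. At 95 to 98% return the split band is 1.6 to 4.2 percentage points wide, and with 90% yes both readings pass at 90% return or more.

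**Conclusion.** No change to the plan is needed. The gap is one of detail, in a descriptive benchmark that carries no test and to which the public text attaches no further decision. An analyst would most naturally report the percentage among those who answered, because attrition already has its own outcome. Ordinary reporting of the numbers assigned, answering and answering yes in each active condition would let a reader recover either percentage and the two extremes for non-response.

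The size is conditional. The readings conflict only when the responder yes-rate is above 80% and no higher than 80% divided by the return rate: up to 84.2% at 95% return and up to 88.9% at 90%. They agree with complete return, with a yes-rate at or below 80%, or with a yes-rate above that upper limit. Return rates, yes-rates and numbers per condition are assumptions throughout. The conclusion also rests on the public text, which refers to a Study Population section that it does not include, although the Acceptability paragraph appears complete. The efficacy conclusions do not depend on this figure.
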